## V. FLOW CHART AND SCHEDULE OF ASSESSMENTS

### Flow Chart

#### Primary Study Period: Screening/ICF through 12-months post-transplant (Day 365/Visit 14)

1. Screening visit and V2 (first dose) may occur either separately or on the same day. Eligibility will be determined using local laboratory results collected at the screening visit. The first dose of study drug must be administered prior to conditioning therapy. The dosing interval in relation to transplant/conditioning must be maintained.
2. Local laboratory assessments may be repeated 1 time if abnormal within the 25 day screening period.
3. The subject may be rescreened 1 time if the transplant is delayed and it will be outside the 25 day screening window. If outside the 25 day screening period, all screening procedures must be repeated.
4. Baseline is date of first dose (V2). The day of transplant (donor cell infusion) is day 0 and all visit days are relative to day 0.
5. Note that the day 365 visit must occur on day 365 +14 days (between day 365 to 379); it cannot occur prior to day 365.

#### Long-term Follow-up Period: Primary Study Period Completion through Long-term Follow-up Completion (Day 365/Visit 14 through 5.5 years Post-Transplant)

| Long-term Follow-up Contact + |
|--|--|--|--|--|--|
| 1.5 Years Post-Transplant                | 2 Years Post-Transplant                  | 3 Years Post-Transplant                  | 4 Years Post-Transplant                  | 5 Years Post-Transplant                  | 5.5 Years Post-Transplant                |
| 18 Months                                | 24 Months                                | 36 Month                                 | 48 Months                                | 60 Months                                | 66 Months                                |

\* Subjects will be contacted after the last injection of vaccine through 5.5 years post-transplant for long-term safety related to the DNA vaccine. Items to be assessed by telephone interview, and available patient records include; mortality, development of any new/recurrent cancer, development of infection requiring hospitalization or resulting in death, and erythema and induration at the injection site [Appendix 20](#).

**Table 1 Schedule of Assessments – Primary Study Period Visit 1 (Screening) – Day 365**

	Screening 	Dose 1  (Baseline)		Transplant 	Dose 2		Dose 3		Dose 4		Dose 5			Primary Study Period Completion / Early Termination Visit 	
Visit Number	V1 	V2 	V3 	V4	V5 	V6 24*	V7	V8	V9	V10*	V11	V12*	V13	V14	
Day Relative to Transplant or Prior Dose	-30 to -5	-14 to -3	Follow-up Dose 1 +10 to 14 days	0	14-40	Follow-up Dose 2 +10 to 14 days	60	Follow-up Dose 3 +10 to 14 days	90	Follow-up Dose 4 +10 to 14 days	100	180	Follow-up Dose 5 +10 to 14 days	270	365
Visit Window							±5 days		±10 days			±10 days		±10 days	+ 14 days (between Day 365 to 379)
Month	-1			0	1		2		3			6		9	12
Assessments															
Informed Consent 	X														
Subject Number Assignment 	X														
Inclusion/Exclusion Assessment	X	X P													
Medical History & Demographics	X	X P													
Clinical Evaluation (Physical Exam & Vitals) 	X	X P			X P		X P		X P			X P		X	X
Concomitant Medication Review 	→														
Safety Laboratory 	X	X			X P	X	X P	X	X P	X		X P	X		
CMV Screening Serology 	X														
Modified HCT-CI Score 	X														
Pregnancy Test (females) 	X	X P			X P		X P		X P			X P		X	X
Adverse Event and SAE Review 	→														
Randomization		X P													
Health Economic Assessment (HEA)	→														
EQ-5D, FACT-BMT, WPAI 		X P			X P		X P		X P			X P		X	X
Immunogenicity Laboratory 		X P			X P			X	X P			X P			X

Table continued on next page

	Screening 	Dose  (Baseline)		Transplant 	Dose 2		Dose 3		Dose 4		Dose 5			Primary Study Period Completion / Early Termination Visit 	
Visit Number	V1 	V2 	V3 	V4	V5 	V6 24*	V7	V8	V9	V10*	V11	V12*	V13	V14	
Day Relative to Transplant or Prior Dose	-30 to -5	-14 to -3	Follow-up Dose 1 +10 to 14 days	0	14-40	Follow-up Dose 2 +10 to 14 days	60	Follow-up Dose 3 +10 to 14 days	90	Follow-up Dose 4 +10 to 14 days	100	180	Follow-up Dose 5 +10 to 14 days	270	365
Visit Window							±5 days		±10 days		±10 days		±10 days	+ 14 days (between Day 365 to 379)	
Month	-1			0	1		2		3		6		9	12	
Platelet count 		X P			X P		X P		X P		X P				
Pharmacogenomics (PGx) – (Optional) 		X P													
CMV Plasma Viral Load Testing 				Start Weekly Testing; See Table 1a							Every Other Week	Every 30 days			
Study Drug Injection 		X 			X		X		X		X				
Local Reactogenicity Assessment 		X			X		X		X		X				
Transplant Information 				X											
DONOR Blood Sample (Optional) 				X											
Karnofsky Performance Scale		X			X		X		X		X		X	X	
aGVHD and cGVHD  (See Table 1a )					X		X		X		X		X	X	

P = procedure to be completed prior to dosing \* = Visit procedures may be performed by Home Health Care (HHC), if applicable in the country. Note: When CMV Plasma Viral Loads fall outside of a regular clinic Visit, the blood draw may be performed by HHC.

**Table 1a CMV Plasma Viral Load Testing (Central Laboratory) and GVHD Assessments**

Assessment Number	V4 Transplant	A1	A2	A3	A4	A5	A6	A7	A8	A9	A10	A11	A12	A13	A14	A15	A16	A17	A18	A19	A20	A21	A22	A23	A24	A25	
	Day 0	Day 7 Week 1	Day 14 Week 2	Day 21 Week 3	Day 28 Week 4	Day 35 Week 5	Day 42 Week 6	Day 49 Week 7	Day 56 Week 8	Day 63 Week 9	Day 70 Week 10	Day 77 Week 11	Day 84 Week 12	Day 91 Week 13	Day 98 Week 14	Day 112 Week 16	Day 126 Week 18	Day 140 Week 20	Day 154 Week 22	Day 168 Week 24	Day 198	Day 228	Day 258	Day 288	Day 318	Day 348	
Visit Window (days)		±4	±2	±2	±2	±2	±2	±2	±2	±2	±2	±2	±2	±2	±2	±5	±5	±5	±5	±5	±5	±5	±5	±5	±5	±5	±5
CMV 		X	X	X	X	X	X	X	X	X	X	X	X	X	X	X	X	X	X	X	X	X	X	X	X	X	X
aGVHD 		X	X	X	X	X	X	X	X	X	X	X	X	X	X												

Note: When CMV Plasma Viral Loads fall outside of a regular clinic visit, the blood draw may be performed by HHC.

1. Informed consent must be obtained prior to the performance of any study-related procedure and before randomization.
2. Screening procedures may be completed -30 to -5 days prior to the day of transplant. Local laboratory results are to be used for screening purposes. The screening laboratory results may be repeated 1 time throughout the noted period. The subject may be rescreened 1 time if the transplant is delayed and it will be outside the 25 day screening window. If outside the 25 day screening period, all screening procedures must be repeated.
3. Subjects will be assigned a subject number for use throughout the study at the screening visit via the Interactive Response Technology (IRT) system.
4. Screening visit and V2 (first dose of study drug) may occur either separately or on the same day.
5. A complete physical examination (PE) will be conducted at the screening (V1) and at the primary study period completion/day 365 visit (V14). At all other visits where a PE is performed, symptom-directed PEs may be done. A detailed description of the subject's current disease status and conditioning regimen (including doses) will be recorded at the baseline visit (V2). The evaluations conducted at each visit are to be performed by the Investigator or qualified medical personnel who routinely perform these evaluations in this subject population. Vital signs will be collected immediately prior to injection and 60 (±10) minutes post injection (except weight) at study visits accompanied by injection and once at screening (V1), and at V13 & 14. Vital signs include blood pressure, pulse rate, respiratory rate, temperature and weight. Height will be collected at the screening visit. Performance status will be assessed using the Karnofsky Performance Scale (KPS) at baseline visit (V2).
6. All concomitant medications and therapies administered from 30 days prior to transplant through 30 days post last dose of study drug will be collected on the electronic case report form; Concomitant medications and therapies associated with Grade 3 and higher grade adverse events (AEs) as well as all serious adverse events (SAEs) will be collected from 31 days post last dose of drug through 1 year post-transplant. Over-the-counter medications, and herbal remedies do not need to be captured beginning 30 days after the last dose of study drug.

Footnotes continued on next page

7. Safety Laboratory will be drawn at the screening visit using the local laboratory. Safety laboratory will be done by a central laboratory at baseline, before doses 2-5, and at each follow-up time point for doses 2-5, and will include hematology and biochemistry, including a hepatic profile. Please refer to [Protocol Appendix 1] for a full list of routine safety parameters that will be tested, and to [Section 5.4.3] and the Laboratory Manual for further instruction on laboratory collection and processing.
8. Screening for cytomegalovirus (CMV) immunoglobulin G (IgG) seropositivity by the local laboratory may be performed up to 30 days prior to transplant and before randomization.
9. The modified hematopoietic cell transplant-comorbidity index (HCT-CI) score are to be completed during screening with history and laboratory from the screening visit. Local laboratory results are to be used in the assessment. Local laboratories may be repeated once to score the HCT-CI. Pulmonary function tests (PFTs) including forced expiratory volume (FEV1) and diffusing lung capacity of carbon monoxide (DLco), multi gated acquisition scan (MUGA), and/or echocardiograms performed within 6 months (180 days) prior to screening are to be used for scoring pulmonary and cardiac comorbidities. PFTs (FEV1 and DLco), MUGAs /or echocardiograms not performed within 6 months of screening will have to be repeated for scoring purposes.
10. For all females of childbearing potential and all females who are of non-childbearing potential but are < 50 years of age and not documented to be surgically sterile, a urine or serum pregnancy test will be performed at screening, on the same day and prior to each dose, at visit 13, and at the primary study period completion/day 365 visit (V14). All pregnancy tests will be done locally. For subjects who receive mycophenolate mofetil, additional pregnancy testing should be done in accordance with local regulatory requirements.
11. All AEs and SAEs will be collected from signing of the informed consent through 30 days post last dose of study drug. All events requiring adjudication (CMV end organ disease [EOD], initiation of CMV-specific antiviral therapy [AVT], and cause of death), grade 3 and higher grade AEs as well as all SAEs will be collected from 31 days post last dose of drug through 1 year post-transplant. A change in medical status or medical history from time of signing of informed consent through first dose of study drug is to be reported as an AE or SAE as applicable. In this study, the day 0 HCT is not considered an AE.
12. The EuroQol – 5D (EQ-5D), Functional Assessment of Cancer Therapy – Bone Marrow Transplant (FACT-BMT), and Work Productivity and Activity Impairment Questionnaire (WPAI) are to be completed by the subject prior to any other study assessments or visit procedures. Subjects are to complete these assessments in the following order: EQ-5D first, FACT-BMT second, WPAI:GH last. For all 3 patient-reported outcome measures, i.e. EQ-5D, FACT-BMT, WPAI, the answers must come from the subject. If the subject is unable to fill out the questionnaire, the assessment should not be performed. If the subject is unable to answer a question, the rest of the questionnaire still needs to be completed.
13. Immunogenicity laboratories include collection of blood for the glycoprotein B (gB) antibody and phosphoprotein 65 (pp65) T-cell assays. Samples are to be drawn on visits V2, V5, V8, V9, V11 and V14. Samples for T-cell assays will not be collected if the absolute lymphocyte count is known to be < 500 mm^3 by local or central laboratory measurement. If the visit coincides with a study drug administration, the sample will be drawn prior to injection.
14. The platelet count must be at least  $\geq 50000$  mm^3 (spontaneously or after platelet transfusion) performed by the local laboratory within 3 days prior to all study drug injections. Prior to all study drug injections, confirmation must be made that there is no medical contraindication to an IM injection. Results received in an equivalent local unit of measure must be converted to SI units. If the subject's platelet count does not meet this threshold at the time of the visit, the subject may return for the study drug injection and local reactogenicity assessment at a later time within the allowable window for the visit. If the subject's platelet count does not meet this threshold during the visit window, the dose must be skipped and the corresponding follow-up safety laboratory and reactogenicity assessment should not be done. The second injection should be given as close to, but not prior to, day 14 as possible.
15. Subjects who consent to participate in the pharmacogenomics (PGx) substudy will have a saliva sample collected during the baseline visit (V2), after randomization but prior to the first dose of study drug.
16. Plasma viral load by the central laboratory will be monitored weekly ( $\pm 2$  days) during days 0-100, every other week ( $\pm 5$  days) during days 101-180, every 30 days ( $\pm 5$  days) during days 181-365, at the initiation of CMV-specific AVT, when clinically indicated, and every time a viral load sample is sent to the local laboratory. When CMV-specific AVT is initiated, a central CMV viral load will be obtained a minimum of weekly until CMV-specific AVT is discontinued. Thereafter, the regularly scheduled viral load assessments will resume according to the scheduled protocol assessments.

*Footnotes continued on next page*

17. The first dose is to be given at day -14 to -3 prior to transplant and within 72 hours prior to the start of chemotherapy and radiation therapy for conditioning.
18. The subject must be monitored directly for the first 15 minutes of the injection. The subject must be in the clinic, but does not require direct monitoring, from 15 minutes through 1 hour after the injection.
19. Local reactogenicity will be evaluated 1 hour ( $\pm$  10 minutes) after each injection and for each of the 7 consecutive days following each injection beginning approximately 24 hours following each dose (day 1-7 postdose). The assessments for each of the 7 consecutive days following an injection will be done by the subject and reported to the site via diary. When reactogenicity is reported as an AE, it is to be followed until resolution or medically stable. All local reactions  $\geq$  grade 3 [Appendix 7](#) require confirmation by a health care professional.
20. The date of transplant (donor cell infusion) defines day 0 and all visit days are relative to day 0. Based on this schedule, V3 may occur prior to or after the day of transplant, day 0.
21. Transplant information includes recipient transplant volume infused, HLA typing of the donor and recipient, HLA cross match at time of transplant (as determined by the site's standard method of determination and, if available), type of transplant, the number of CD34+ stem cells/kg infused if available, donor and recipient CMV serostatus, if available the hepatitis B virus (HBV) serostatus, hepatitis C virus (HCV) serostatus, and Epstein Barr Virus (EBV) serostatus of the donor and recipient; blood type of the donor and recipients. ABO cross match (if available), donor-recipient relatedness, donor gender, age, race (if available) and ethnicity (for the USA only and if available); donor product plasma; volume and RBC depletion status; and if available donor cell product CD3+, CD4+, CD8+ and CD56+ cell counts. For bone marrow recipients, the number of mononuclear cells transfused must also be included, if possible.
22. *Optional:* A 20 mL peripheral blood sample from the CMV seropositive donors will be obtained prior to the stem cell donation for recipients participating in the main trial to test for CMV-specific T-cells (requires donors' consent). For those donating peripheral stem cells, the donor blood sample is to be collected prior to the initiation of mobilization therapy (e.g., G-CSF). Not applicable to sites in Japan.
23. Acute and chronic GVHD is to be assessed and graded/globally scored and the KPS will be used to assess performance status at baseline and V5, V7, V9, V11, and V13 following transplant (day 0) through the primary study period completion/day 365 visit (V14) except when the visit is conducted by HHC. In addition, aGVHD needs to be assessed weekly through day 100. When a diagnosis of aGVHD is made for a subject, assessments are to continue weekly until resolution for maximal grade and stage by key organs. Local laboratories may be used for staging. When a diagnosis of cGVHD or aGVHD is made by a health care professional for a subject, the subject should return to the study center for evaluation and data collection, and assessments are to be done at each regularly scheduled protocol visit until resolution; the maximum score during the interval from the last assessment to the current assessment is to be recorded for assessments performed at the study site.
24. If the subject does not meet the criteria for dosing by day 40, V5 procedures (except study drug injection and local reactogenicity assessment) need to be completed within 5 days of day 40 (day 40 to 45) and V6 should be skipped.
25. The day 365 visit must occur on day 365 +14 days (between day 365 to 379); it cannot occur prior to day 365 for subjects who do not prematurely withdraw from both treatment and continued follow-up. For a subject who prematurely withdraws from the study (discontinues treatment with no continued follow-up), the study completion visit is to be completed within 14 days of study withdrawal.

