### 3.3 Exclusion Criteria

A subject will be excluded from participation if any of the following apply:

1. Subject has active CMV disease or infection or has received treatment for active CMV disease or infection within 3 months (90 days) prior to transplant.
2. Subject has planned CMV prophylactic therapy with antiviral drugs or CMV-specific immunoglobulins from randomization through the primary study period completion/day 365 visit (V14).
3. Subject has a modified hematopoietic cell transplant comorbidity index (HCT-CI) score  $\geq 4$  Appendix 4.
4. Subject is known to be positive for human immunodeficiency virus (HIV), hepatitis B surface antigen or hepatitis C RNA PCR.
5. Donor CMV serostatus is unknown.
6. Subject has received any of the following substances or treatments:
  - a. Alemtuzumab within 60 days prior to transplant, including conditioning regimen. Subjects for whom treatment with alemtuzumab is planned at any time from 60 days prior to through 1 year post-transplant must not be enrolled in the trial.
  - b. T-cell depletion of donor cell product.
  - c. Administration of a CMV vaccine, including any prior exposure to ASP0113.
7. Subject has received an allogeneic stem cell transplant within 1 year prior to transplant (subjects who have received a prior autologous transplant are allowed).
8. Subject has a current malignancy in addition to the malignancy being treated for the study or the subject has a history of any other malignancy (within the past 5 years prior to screening) except non-metastatic basal or squamous cell carcinoma of the skin that has been treated successfully or cancer in situ of the cervix uteri that has been handled by local surgery.
9. Subject has an unstable medical or psychiatric condition, including a history of illicit drug(s) or alcohol abuse that the Investigator believes will interfere with protocol requirements.
10. Subject has had an allergic reaction to any component of the vaccine. Subject has had an allergic reaction to aminoglycosides as kanamycin is used in the manufacturing process of the vaccine.

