#### **5.1.5.2 Concomitant Medication (Drugs and Therapies)**

All concomitant medications and therapies administered from 30 days prior to transplant through 30 days post last dose of study drug will be collected on the eCRF; Concomitant medications and therapies associated with all events requiring adjudication, Grade 3 and higher AEs as well as all SAEs will be collected from 31 days post last dose of drug through 1 year post-transplant. Over-the-counter medications, and herbal remedies do not need to be captured beginning 30 days after the last dose of study drug.

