### **5.1.5.3 Prohibited Concomitant Medications (Drugs and Therapies)**

The following medications and therapies are prohibited throughout the study (through the primary study period completion/day 365 visit [V14]):

- Investigational research products that have not been approved for any indication in the country where the subject is enrolled.
  - New regimens of approved chemotherapeutic drugs or antibodies; conditioning drugs, irradiation and T-cell depleting antibodies, except alemtuzumab, are allowed.
- Prophylactic use of antiviral drugs for CMV viremia from time of randomization through completion of the primary study period completion/day 365 visit (V14).
- Prophylactic use of CMV-specific immunoglobulin.
- Alemtuzumab within 60 days prior to transplant (including conditioning regimen) through completion of the primary study period completion/day 365 visit (V14) unless required for disease relapse post-transplant.

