2. Screening procedures may be completed -30 to -5 days prior to the day of transplant. Local laboratory results are to be used for screening purposes. The screening laboratory results may be repeated 1 time throughout the noted period. The subject may be rescreened 1 time if the transplant is delayed and it will be outside the 25 day screening window. If outside the 25 day screening period, all screening procedures must be repeated.
3. Subjects will be assigned a subject number for use throughout the study at the screening visit via the Interactive Response Technology (IRT) system.
4. Screening visit and V2 (first dose of study drug) may occur either separately or on the same day.
5. A complete physical examination (PE) will be conducted at the screening (V1) and at the primary study period completion/day 365 visit (V14). At all other visits where a PE is performed, symptom-directed PEs may be done. A detailed description of the subject’s current disease status and conditioning regimen (including doses) will be recorded at the baseline visit (V2). The evaluations conducted at each visit are to be performed by the Investigator or qualified medical personnel who routinely perform these evaluations in this subject population. Vital signs will be collected immediately prior to injection and 60 (±10) minutes post injection (except weight) at study visits accompanied by injection and once at screening (V1), and at V13 & 14. Vital signs include blood pressure, pulse rate, respiratory rate, temperature and weight. Height will be collected at the screening visit. Performance status will be assessed using the Karnofsky Performance Scale (KPS) at baseline visit (V2).
6. All concomitant medications and therapies administered from 30 days prior to transplant through 30 days post last dose of study drug will be collected on the electronic case report form; Concomitant medications and therapies associated with Grade 3 and higher grade adverse events (AEs) as well as all serious adverse events (SAEs) will be collected from 31 days post last dose of drug through 1 year post-transplant. Over-the-counter medications, and herbal remedies do not need to be captured beginning 30 days after the last dose of study drug.

Footnotes continued on next page

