5.3.1 Reasons for Exclusion From PPS

The following reasons may lead to a subject's exclusion from PPS:

- Did not undergo HCT.
- Received different study drug injection from randomized, or study drug is switched during the study
- Administration of prohibited concomitant treatment as described in the Study Protocol.
- Violation of the following inclusion or exclusion criteria which may affect the assessment of the efficacy of the study drug:
 - Inclusion criterion No 3, subject was CMV-seropositive HCT recipient as confirmed by local laboratory at screening.
 - Inclusion criteria No 4 and 5, subject did not undergo 1 of the procedures indicated in these inclusion criteria.
 - Inclusion criterion 6, subject did not have any of the indicated underlying conditions.
 - Inclusion criterion 13, subject participated in another interventional study while on treatment.
 - Exclusion criterion No 1, subject had active CMV disease or infection or had received treatment for active CMV disease or infection within 3 months (90 days) prior to transplant.
 - Exclusion criterion No 6, subject received any of the following substances or treatments:
 - Alemtuzumab within 60 days prior to transplant, including conditioning regimen.
 - T-cell depletion of donor cell product.
 - Administration of a CMV vaccine, including any prior exposure to ASP0113.
 - Exclusion criterion No 7, subject received an allogeneic stem cell transplant within 1 year prior to transplant.
 - Exclusion criterion No 12, subject received a prior HCT and had residual cGVHD.

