7.2.4 Previous and Concomitant Medications

Previous and concomitant medications are coded with WHO-DRL, and will be summarized by therapeutic subgroup (ATC 2nd level) and chemical subgroup (ATC 4th level) and preferred WHO name by treatment group for the FAS and mFAS populations.

Previous medications are defined as medications that patients started and ended prior to first administration of study medication. Concomitant medications are defined as any medications that patients took after the first dose of study medication and through 1-year post-transplantation (i.e., 380 days from transplantation). Any previous medications that continued while study drug was given will be counted as both previous and concomitant medications.

Subjects taking the same medication multiple times will be counted once per medication and investigational period. A medication which can be classified into several chemical and/or therapeutic subgroups is presented in all chemical and therapeutic subgroups.

Antiviral therapies, including those used for reasons other than CMV infection, are of special interest. These medications will be summarized by reason for use.

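### Full medication recording stops 30 days after each subject's last dose, while the antiviral limits run to day 365 and the SAP's by-arm medication tables to day 380

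*Protocol*

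**What the plan says.** **Collection.** Protocol Table 1 footnote 6, repeated in the SAP's Table 1, sets the period of full recording: "All concomitant medications and therapies administered from 30 days prior to transplant through 30 days post last dose of study drug will be collected". A narrower rule follows in the same footnote: "Concomitant medications and therapies associated with Grade 3 and higher grade adverse events (AEs) as well as all serious adverse events (SAEs) will be collected". This second phase starts on day 31 after the last dose and ends at 1 year. Protocol 5.1.5.2 has the same cut-off but a wider second phase: "Concomitant medications and therapies associated with all events requiring adjudication, Grade 3 and higher AEs as well as all SAEs will be collected". Footnote 11 lists the adjudicated events as CMV end organ disease, initiation of CMV-specific antiviral therapy (AVT), and cause of death.

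**Rules that run longer.** Protocol 5.1.5.3 prohibits CMV antiviral prophylaxis from randomization through V14. Section 5.1.5.2.2 caps prophylactic aciclovir, valaciclovir and famciclovir from transplant through day 365.

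**Analyses that run longer.** SAP 7.2.4 says "Concomitant medications are defined as any medications that patients took after the first dose of study medication and through 1-year post-transplantation" and puts the end at day 380. It asks for all antivirals, whatever the indication, to be summarized by reason for use. The SAP revision history (8.1) gives the aim of the medication summaries as looking for confounding of the efficacy results. SAP 5.3.1 lists as a reason for leaving the per protocol set (PPS): "Administration of prohibited concomitant treatment as described in the Study Protocol".

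**The concern.** Prophylaxis is by definition given before infection is detected, so it usually has no adverse event to attach to. It is the class that SAP 7.2.4 singles out, and the class that the restricted phase is least likely to capture.

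The cut-off is also not a fixed date. It follows the last dose, which is a post-randomization outcome. Doses are skipped for low platelets (protocol 5.1.1) and stopped for failure to engraft or severe local reactions (3.5), while follow-up continues. Subjects with the fewest doses lose full recording earliest but stay in the efficacy analyses.

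At stake is whether the by-arm antiviral table can do the job the SAP gives it, and whether screening for prohibited drugs in the PPS is equally complete for all subjects.

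**Working it through.** The plan states no figure for this gap, so there is nothing to reproduce. The check is direct arithmetic.

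**Inputs**
- Full recording ends on last dose day *d* + 30 (footnote 6; protocol 5.1.5.2).
- Dose windows (protocol 5.1.1): days -14 to -3, 14 to 40, 60 ± 5, 90 ± 10, 180 ± 10.
- Horizon *H*: 365 for the protocol limits, 380 for SAP 7.2.4.

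**Formula.** Restricted days = *H* - (*d* + 30); share = restricted days / *H*. This assumes a subject followed to the horizon.

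| Last dose | Dose day | Full recording ends | Restricted days to 365 | Share |
|---|---|---|---|---|
| 1 | -14 to -3 | 16 to 27 | 349 to 338 | 95.6% to 92.6% |
| 2 | 14 to 40 | 44 to 70 | 321 to 295 | 87.9% to 80.8% |
| 3 | 55 to 65 | 85 to 95 | 280 to 270 | 76.7% to 74.0% |
| 4 | 80 to 100 | 110 to 130 | 255 to 235 | 69.9% to 64.4% |
| 5 | 170 to 190 | 200 to 220 | 165 to 145 | 45.2% to 39.7% |

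For dose 5 on day 180: 365 - 210 = 155 days, and 155/365 = 42.5%.

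On the day-380 horizon, dose 5 gives 160/380 = 42.1% to 180/380 = 47.4%, and dose 1 only gives 353/380 = 92.9% to 364/380 = 95.8%.

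**Sensitivity to unequal dosing.** Full recording ends on day 210 for dose 5 on day 180, and on day 16 to 27 for dose 1 only. Each percentage point of subjects moved from the first pattern to the second shortens an arm's mean full-recording period by (210 - 27)/100 = 1.83 to (210 - 16)/100 = 1.94 days. The documents give no expected dosing pattern by arm, so the net difference cannot be computed.

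**What falls out.** Setting the rules side by side:
- Initiation of CMV-specific AVT: kept to 1 year as an adjudicated event (footnote 11).
- Any drug tied to a grade 3+ AE or an SAE: kept to 1 year.
- Drugs tied to an adjudicated event: kept under 5.1.5.2, not under footnote 6. This is a contradiction.
- Prophylaxis started within the full-recording period: kept.
- Prophylaxis first started, or changed in dose, after the cut-off without a qualifying event: not required on the eCRF.

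**The case against.** The case against has force on several points.

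- **Collection does not stop.** A reader might infer that no medication is recorded after the cut-off and that prohibited drugs become invisible. The documents do not support that. Qualifying medication "will be collected from 31 days post last dose of drug through 1 year post-transplant", and AVT initiation is collected separately. The shares above are time under restricted recording, not time without data.
- **Prohibited drugs have another route.** Protocol 8.1.6 makes excluded concomitant treatment a notifiable deviation with no 30-day limit, and SAP 7.2.2 tabulates it as PD4. PPS decisions are made at a blinded review and are not tied to the medication page. It is therefore too strong to say that PPS membership simply mirrors dosing history. What stands is that PD4 depends on someone noticing, and that it does not supply the drug, dose and reason that an antiviral table needs.
- **Early prophylaxis is still counted.** SAP 7.2.4 counts a subject once per medication and investigational period, and a wholly missing stop date is imputed far into the future (SAP 7.10.1). A subject stopped after dose 1 does not therefore appear free of prophylaxis that began around transplant. The loss is confined to later starts and dose changes.
- **The look-back is not a fault.** A reader might set the 30-day medication look-back against the 60-day alemtuzumab rule and the rule for a subject who "has received treatment for active CMV disease or infection within 3 months (90 days) prior to transplant". Those are eligibility criteria, checked at V1 and V2. Protocol 5.2.2 requires the history of prior CMV, and SAP 5.3.1 treats breaches as eligibility violations. The medication look-back does not govern them.
- **Both arms share one rule.** A distortion between arms needs unequal dosing, and no figure for that exists. Phase 2 local reactogenicity (22.9% against 10.9%, protocol 1.3.2.2) shows a possible route, not a size.

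**Conclusion.** The concern holds in a limited form. The medication record is shorter than the rules and tables that use it, by 40-45% of days 1-365 for a subject with an on-schedule dose 5 and by 93-96% for one with dose 1 only. The upper range applies only to subjects with no further dose, and the documents do not say how many to expect.

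Two consequences follow. The by-arm antiviral table in SAP 7.2.4 partly reflects dosing history. After the cut-off, detection of prohibited drugs for the PPS rests on PD4 reporting unless a qualifying event brings the drug onto the record. Separately, footnote 6 in both documents contradicts protocol 5.1.5.2 on events requiring adjudication.

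The effect on conclusions is bounded. The primary analysis is a CMH test of death or adjudicated end organ disease in the full analysis set and uses no medication data. First adjudicated AVT use is also unaffected. The 7.2.4 tables are descriptive and the PPS analyses supportive. This is a cheap improvement, not a threat to the main result.

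**What to change.** 1. Amend footnote 6 in both documents, and protocol 5.1.5.2, so that systemic antivirals (with dose and reason), CMV immunoglobulin and prohibited agents are recorded through V14 for every subject, whatever the date of the last dose and with or without a linked event.
2. Reconcile footnote 6 with 5.1.5.2 on medication tied to events requiring adjudication.
3. In SAP 7.2.4, limit the tables for all other drug classes to the full-recording period and label them so. If collection can no longer be changed, do the same for antivirals, before unblinding.

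The cost is a small data-entry burden for a short list of drug classes. No visit or procedure is added: V13 and V14 already exist, and sites already review medical records through V14 for the health economic assessment (protocol 5.3.8.4). Item 3 alone needs only SAP wording, but it would leave late antiviral use undescribed.
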